### C. Innovation

Health information technology (HIT) is rapidly evolving, and adoption is increasing in efforts to improve access to, efficiency of and effectiveness of care. More and more health care systems are using HIT to not only assist with basic patient care, but also to improve decision support, foster quality improvement, and improve code status documentation. Given physicians' difficulties in identifying patients near the end of life, and the role poor prognostication plays in disparities in palliative care and hospice use, this proposal to harness data in the EMR to create a computerized e-EOL algorithm represents a next generation application of HIT to create intelligent decision support to assist physicians in identifying advanced cancer patients who would benefit from a discussion about EOL care options. This novel computerized algorithm will not only systematically identify all eligible patients; it will do so in real time, when the intelligence is actionable. While EMR-based screening algorithms have been effective in many areas, no study to our knowledge has applied these tools to identifying cancer patients at the end of life. The multi-component intervention we will develop and test has several innovative features including: 1) creation of novel, culturally tailored messages and DVD modules on concerns about spirituality and medical mistrust to overcome key barriers to EOL use among AA patients, 2) use of a non-medical, culturally concordant lay health advisor (LHA) to bolster trust and facilitate shared decision-making about EOL options, 3) adaptation of an existing EOL education DVD designed for use in majority populations to AA patients, and 4) HIT implementation of the e-EOL screening algorithm to identify potentially eligible cancer patients in real-time. Collectively, this work will provide the foundation for an R01 application to conduct a fully powered randomized controlled trial (RCT) to evaluate the effectiveness of this patient-centered, multi-component intervention versus usual care.

### D. APPROACH

#### D.1 PRELIMINARY STUDIES

Several pilot studies provide a solid foundation for the proposed research. To establish the feasibility of using EMR data to identify patients with advanced cancer, we have developed a preliminary electronic (e-EOL) algorithm adapting applied medical informatics approaches that [name] and others at UTSW have successfully used in prior studies. To date, a prototype *inpatient* e-EOL algorithm has been piloted for patients with advanced lung and breast cancer based on the ICD-9 codes displayed in Table 1. A total of 369 breast and lung cancer patients were hospitalized at Parkland Hospital from 2009 – 2010. Of those, 14% were flagged by the algorithm as meeting national guideline criteria as most appropriate for an in-depth discussion about EOL care options. Of those identified, 39% had breast cancer and 58% had lung cancer. The e-EOL algorithm identified 53 (14%) patients that met assigned criteria (presence of metastatic disease and albumin < 2.5 g/dl), while physician chart abstractors felt that 64% of patients met criteria indicating a need for in-depth discussion about EOL care options. Over half (55%) of those identified by the e-EOL algorithm were African American (19% were white, and 25% Hispanic). When compared to physician chart review (the criterion gold standard), the sensitivity, specificity, and positive predictive value (PPV) of the pilot algorithm were as follows: 21% (95% CI: 16% to 26%), 96% (95% CI: 93% to 100%), and 91% (95% CI: 83% to 98%) respectively. Thus, this preliminary e-EOL algorithm had very good specificity and PPV and identified many AA inpatients with advanced breast and lung cancer. Additionally, construct validity in the form of survival analysis revealed that patients meeting e-EOL algorithm criteria ("test positive" cases) had worsened survival compared to those

who did not ("test negative" cases) The six month survival rate for test-positive cases versus test-negative cases was 46% (95% CI: 33%-58%) versus 78% (95% CI: 73%-82%) One-year survival for test-positive versus test-negative cases was 32% (95% CI: 20%-45%) versus 72% (95% CI: 67%-76%). More work is being done to improve the sensitivity of the algorithm so we can detect more of the target population. Additionally, UTSW and all of its affiliated hospitals and clinics transitioned to ICD-10 on October 1, 2015, and the algorithm is being replicated with the appropriate ICD-10 codes. Data from the Parkland Tumor Registry corroborates the burden of Stage IV cancer among AAs at Parkland. From 2009-2011 there were 75 patients with stage IV breast cancer, 254 with Stage IV lung cancer, and 135 with Stage IV colorectal cancer. Most advanced cancer patients were AA (57% for breast, 61% for lung, and 55% colorectal cancers, and ranged in age from 30 to 80 years.

We analyzed 11 years of data from the Parkland Hospital palliative care consult service which offers some promising news. From November 1999 to December 2010, 5,267 Parkland patients were seen by the palliative care program, of which, 41% were AA, 31% white, and 24% Hispanic. Once a patient was referred to the palliative care service, there were no racial disparities in referral to and acceptance of hospice services. We attribute this success to a strong multidisciplinary team approach which includes a chaplain, social worker, nurse practitioner, nurse, and four physicians experienced in working with minority patients and their families. This underscores that in our setting the 'quality chasm' in EOL care that needs to be overcome resides predominantly 'upstream', among patients with advanced cancer who have not yet had an informed discussion about their full treatment options including palliative care.

To examine barriers to completion of advance directives, utilization of palliative care, and hospice enrollment among African Americans, we conducted qualitative interviews with African American providers and recipients of hospice or palliative medicine and African American members of the clergy. Semi-structured, videotaped interviews were conducted with 8 African Americans who have had personal and/or professional experience with EOL care. Interviewees included an African American hospice medical director, an African American palliative care nurse practitioner, three African American ministers (one of whom also had experience as a hospital chaplain), one African American hospice patient, and two African American caregivers of patients who had received or were currently receiving hospice care. Several themes regarding barriers to EOL care were confirmed in conducting these interviews, including perceived conflict with spirituality, mistrust in the medical system, and overall lack of knowledge about EOL care options or misunderstanding of the various options. Segments of these videotaped interviews that addressed these specific and previously identified barriers to EOL care among African Americans were selected and combined with culturally sensitive imagery, voice over narration, and text to create a DVD tentatively titled *Planning for the Care You Want*. Palliative care and geriatric medicine faculty and staff who care for patients at Parkland Hospital have vetted the DVD. Additionally, we conducted two focus groups with 16 community-dwelling African Americans who are patients and/or caregivers of patients who receive their care at Parkland Hospital, Clements University Hospital, and their affiliated clinics. These focus group participants were also community religious leaders and members of the UTSW PCOR Community Advisory Panel; they provided feedback on the newly created DVD to determine if the DVD segments conveyed messaging about EOL care options as intended. All groups provided feedback on messaging, duration, and imagery of the DVD that has been used in the editing process.

Taken together, this preliminary work demonstrates the: 1) large numbers of AA patients with advanced cancer at Parkland with substantial unmet needs for counseling about EOL care options, 2) preliminary feasibility of our e-EOL strategy to systematically identify such patients, 3) adequate "downstream" capacity and skill of our existing palliative care service to care for such patients in a culturally-sensitive way once a palliative care consult is formally made, and 3) acceptability of a culturally sensitive DVD that addresses specific barriers to AA EOL care among AA patients, AA caregivers, palliative care providers, and geriatric medicine providers,

## **D.2. Research Design and Methods**

### **D.2.1. Overview of Research Approach**

[figure not shown]
We propose a three-phase project to improve awareness of use of advance directives, palliative care and hospice services among patients with metastatic cancer by creating and evaluating a multifaceted culturally sensitive intervention that targets specific previously identified barriers to EOL care for AAs, including: knowledge, attitudes, and awareness of options for care, conflict between patients' spiritual beliefs,

and the general hospice and palliative medicine philosophy of care, and medical mistrust. Aim 1 will refine and validate the e-EOL computerized algorithm to identify persons with stage III and IV breast, lung, colorectal, and prostate cancer who are appropriate candidates for discussions about advance care planning, palliative care, and hospice in the outpatient setting. The work in Aim 1 seeks to overcome the upstream barrier that physicians often have difficulty with prognostication and are reluctant to discuss prognosis and EOL care options with patients. Aim 2 will involve continued stakeholder engagement and the conduct of focus groups with oncologists and primary care providers at Parkland Hospital and its affiliated clinics to determine how to make the intervention feasible and acceptable to patients, caregivers, and providers. We also will obtain feedback on our newly developed video and written educational materials that communicate key messages about EOL care options and overcome common barriers. In Aim 3, we will test the preliminary feasibility, acceptability, and efficacy of the intervention that uses the e-EOL algorithm to identify AA patients with advanced cancer who are eligible for care discussions and then deploy a culturally concordant behavior change intervention that combines a Lay Health Advisor (LHA) and video and written materials. Of note, patients with earlier stage cancers (I and II) may be chosen for the intervention based on co-morbidities, functional status, or other factors that we deem appropriate. Use of an LHA will help overcome the providers' reluctance or lack of time to discuss EOL care issues and mitigate medical mistrust. The three linked studies provide the necessary sequence of research projects and multidisciplinary learning experiences needed to accomplish the PI's scientific and training goals. It will also lay the groundwork for a fully powered RCT to test the efficacy of a multifaceted EOL care counseling intervention vs. usual care.

**D.2.2. Conceptual Framework: Figure 1**

shows the conceptual model that underpins our design and methods. It is informed by the existing empiric literature, health behavior and implementation science theories, and our prior related work. Our goal is to change patients' stage of intent to discuss EOL care options (primary outcome). We grouped the key factors influencing this outcome by the PRECEDE-PROCEED model.

**Figure 1. Conceptual Framework of Intervention Components and Key Factors Influencing Primary Study Outcome**

**Table 1. Revised e-EOL Algorithm**

Pilot Inpatient Algorithm	ICD-10 Codes	Additional Variables
Breast Cancer	C50.011-C50.929; D05.80-D05.92	
Lung Cancer	C34.10-C34.92; D02.20-D02.22	Albumin < 2.5 gm/dl
Metastases	C77.0 - C79.9	
Outpatient Algorithm	ICD-10 Codes	Documentation of
Breast Cancer	C50.011-C50.929; D05.80-D05.92	ED/Hospital Visits
Lung Cancer	C34.10 - C34.92; D02.20-D02.22	Medications for cancer-related Sx
Colon Cancer	C18.2-C18.9; C19	Radiation Tx
Metastases	C77.0 - C79.9	Chemotherapy

Predisposing factors are patient-level knowledge and attitudes about EOL care, spiritual beliefs, and medical mistrust that are modifiable and are antecedents to our primary study outcome. Reinforcing factors are providers' comfort with EOL care and ability to prognosticate, and patient and caregivers' attitudes toward EOL care. These factors: 1) influence the predisposing factors and 2) provide incentive/opportunity for the primary study outcome. Enabling factors are the intervention resources (e-EOL algorithm, educational DVD modules, and LHA) to facilitate health behavior change. Our intervention addresses the negative attitudes listed under predisposing factors. The DVD segments will role model optimal shared decision-making to help patients build skills so to engage in shared decision-making when communicating about their own EOL care options. The primary behavior change outcome is the intent to discuss EOL care options based on the

“Stages of Change” Transtheoretical Model. The intervention seeks to promote “stage migration” towards a higher level of willingness to discuss EOL care options (See D.5.3. for definitions).

**D.2.3. Study Setting** Parkland Health and Hospital System (Parkland) is a population-based, integrated delivery system that includes: a 900 bed hospital, 12 community-based primary care centers (COPCs), and subspecialty clinics (including onsite palliative care and oncology clinics), which all use the comprehensive, Epic EMR. Parkland is the sole safety net provider in Dallas County, so it is responsible for the care of over one million uninsured individuals and provides \$532 million of uncompensated care annually. It is also the largest teaching site for UTSW medical students, residents, and fellows. Parkland is an ideal setting for disparities research given the large, diverse racial and ethnic populations it serves. Overall, 41% of Parkland patients are AA, 32% Hispanics, 20% White, and 7% other race/ethnicities. All inpatient and outpatient provider notes, diagnoses, orders, medications, laboratory, imaging, and pathology results, referrals, sociodemographics, insurance, and health care utilization information is recorded in the EMR.

**D.3. Details of Research Design and Methods for Aim 1: Refine an e-EOL algorithm to identify patients with metastatic cancer in the outpatient setting.** Aim 1 will expand and validate the e-EOL algorithm to identify patients with Stage III and IV cancer who are appropriate candidates for discussions about EOL care options in the *outpatient* setting. The e-EOL algorithm will assist physicians with determining prognosis more accurately and will provide a mechanism for systematically identifying candidates for a subsequent EOL care counseling intervention outlined in Aim 3.

National guidelines that aid health care providers in determining a patient's eligibility for hospice and EOL option discussions are available, and several national organizations recommend guidelines for the institution of palliative care. The *inpatient* e-EOL algorithm operationalizes the application of hospice guidelines and clinical experience by ‘flagging’ those individuals with advanced cancer meeting guideline criteria for hospice eligibility; however, the *outpatient* e-EOL algorithm will target patients who are earlier in the cancer disease trajectory and would benefit from early palliative care consultation. The preliminary *inpatient* e-EOL algorithm was based on simple ICD-9 codes from the index admission (cancer, metastasis) and albumin measurements; however, UTSW, Parkland and all of their affiliated clinics adopted ICD-10 on October 1, 2015, and the algorithm is now being tested using these updated codes. The *outpatient* algorithm will harness a broadened range of factors contained in discreet fields from the EMR including: patient characteristics (age, race), initial determination of metastatic cancer diagnosis (stage III or IV disease), medications to treat pain and other cancer-related symptoms (opioids/NSAIDs/steroids, anti-emetics, appetite stimulants, antidepressants), processes of care (chemotherapy, radiation therapy), as well as number of ED visits, hospitalizations and ICU stays related to the primary cancer diagnosis. *Albumin < 2.5 mg/dl will not be used in this algorithm as it is a marker of poor prognosis, and we hope to detect patients with metastatic disease earlier in their disease trajectory.* We will explore the impact of different types of Boolean logic combining these factors. We will also broaden our net to include ICD-10 codes in diagnosis, problem lists, and encounter fields of all prior inpatient and outpatient encounters in the past 12 months. Our goal is to increase have sensitivity of the inpatient algorithm of 40-50% and specificity of >90%.

Our approach to validating the e-EOL algorithm in the outpatient setting is based on prior work by [name] and other UTSW investigators which has extracted a complicated combination of EMR data elements to identify patients hospitalized with heart failure, AIDS, and cirrhosis in the first 2 days of admission. For example, the heart failure algorithm used data on admitting diagnoses and co-morbidities (from index and prior inpatient and outpatient encounters), labs, vital signs, and notes (chief complaint symptoms and imaging results).

Most research in this area relies on administrative data and diagnoses to identify cases **after the fact**. For the e-EOL algorithm to be actionable, it needs to flag a patient *early in their advanced disease stage* so that counseling about EOL care options (and a potential palliative care consultation) can occur. A recently completed study by researchers here proves our ability to automatically identify cases in real time using an EMR-based algorithm, and successfully deployed an intervention that reduced the risk of readmission. As we did in our pilot project, three board certified internal medicine physicians and experts in hospice, palliative medicine and/or geriatrics will independently perform implicit and explicit chart reviews of each “test positive” and “test negative” case to make the criterion standard judgment about whether the patient meets criteria for hospice eligibility based on the national guidelines and clinical experience. All reviewers will undergo training on the process and criteria to be judged, and practice reviews on selected advanced cancer “positive”

and “negative” cases to help them develop a shared understanding. Once the training is completed, two reviewers will independently review the EMR for each case and render a final judgment about whether the patient: 1) has Stage III/IV breast, lung, colon, prostate or other advanced cancer, and 2) meets guideline criteria for being eligible for an EOL care options discussion. Initial agreement and Kappa scores will be computed, and areas of disagreement will be resolved by discussion. The third reviewer will be used if consensus cannot be reached. Sensitivity, specificity, and positive/negative predictive values for the algorithm will be calculated. The e-EOL algorithm results define “test positivity” and physician chart review as the criterion standard (denominator). The e-EOL algorithm will be iteratively refined to improve its test operating characteristics. For the purposes of this project, assuring adequate specificity (80-90%) will be more important than optimal sensitivity (40-50%).

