**Aim 1: Validate a computerized (e-EOL) algorithm using EMR data to identify patients in the outpatient setting with advanced breast, lung, and colorectal cancer who are appropriate for advance care planning, palliative and EOL care discussions (to be referred to moving forward as EOL care options).**

**Hypothesis 1:** An IT-enabled electronic algorithm is currently being developed that will identify inpatients at Parkland Hospital who have advanced breast, lung, and colon cancer who would be most appropriate for counseling about EOL care treatment options. We plan to validate a similar algorithm for patients with metastatic (Stage III/IV) breast, lung, colon, prostate, or other advanced cancer in the outpatient setting so that it will have sufficient sensitivity, specificity, and positive predictive value.

**Aim 2: Refine a culturally sensitive intervention to increase knowledge about, reduce barriers and promote intention to discuss EOL care options among AA advanced breast, lung, and colon cancer in the outpatient setting.**

**Hypothesis 2:** A combination of DVD modules describing facts about EOL care and testimonials by AA patients, caregivers, physicians, and religious leaders, together with scripted counseling by a trained, culturally concordant lay health advisor will effectively improve knowledge and address barriers to receipt of EOL care (perceived conflict with spiritual beliefs and medical mistrust). These materials will be vetted by a group of outpatient primary care and oncology providers at Parkland Hospital.

**Aim 3: Test the feasibility and acceptability of a theory-based, multifaceted pilot program that will identify AA patients with metastatic breast, lung, colon, and prostate cancer via the outpatient e-EOL algorithm and then test the preliminary efficacy of a culturally sensitive, patient-centered intervention to change knowledge and barriers about and intent to discuss EOL care options by conducting a small, pilot randomized controlled trial (RCT).**

**Hypothesis 3:** An EMR-enabled, culturally sensitive, outpatient-based intervention targeting knowledge, beliefs, and behavioral intentions will be feasible and acceptable to AA patients and will result in increased willingness to discuss EOL care options versus a usual care control group. Patients with earlier stage cancers (I and II) may be chosen for the intervention based on co-morbidities, functional status, or other factors that we deem appropriate.

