**D.5.1. Study Subject Identification and Enrollment:** We will use the refined e-EOL algorithm in real-time to identify AA patients with Stage III or IV breast, lung, colorectal, prostate, or other advanced cancer for EOL care counseling. The e-EOL algorithm will run once every day to flag potentially eligible candidates using an IT protocol used successfully in previous intervention research at Parkland. The eligibility criteria are the same as those outlined in D.4.1. (AAs,  $\geq 21$  years, with advanced breast, lung or colon cancer, are English proficient, competent, cognitively intact by Mini-cog test, and no prior palliative care consult or receiving palliative care). Patients with earlier stage cancers (I and II) may be chosen for the intervention based on co-morbidities, functional status, or other factors that we deem appropriate. The research assistant will contact the patients' physicians to confirm eligibility and get permission to introduce the study to the patient. Once eligibility is confirmed, the research assistant will introduce the study to the patient, obtain informed consent, and administer the pre-intervention survey and needs assessment (described below). Each patient will be asked to identify a primary caregiver that will be able to participate in the intervention. Caregivers must be: 1) identified by the selected patient, 2)  $\geq 21$  years of age, 3) English proficient, and 4) competent to participate. The research assistant will then notify the EOL LHA of any study participants. The EOL LHA will contact each patient's primary caregiver by phone to confirm their participation in the study, and arrange a time to meet with both the patient and caregiver to conduct the intervention. We will recruit up to 60 patients and their caregivers, if a caregiver is available to participate, to allow us to pilot the intervention and sort out logistics of administering the intervention in a clinical setting prior to randomization. Overall, at least 48 patient-caregiver pairs will be randomized in the study representing an approximately even distribution across different cancer diagnoses. Twenty-four patient-caregiver pairs will be randomized to the intervention arm of the study, and twenty-four will be randomized to the usual care control group.

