**D.5.4. Statistical Analysis Plan:** We will use descriptive statistics to characterize study participants and proportion of intervention elements and follow-up assessments completed. The specificity and positive predictive value of the e-EOL algorithm operating in real world practice will be assessed using methods described for Aim 1 with physician chart review as the criterion standard. Acceptability and feasibility process data will be tallied. The main decision making outcome will be *change in the stage of intent to discuss EOL care options* from baseline through all follow-up intervals. Movement to an adjacent stage is a 1 point change. We will assess several aspects of stage change based on the proportion of patients at each time interval showing: 1) *any* stage pro/regression, and 2) *full progression* to the action stage of discussion EOL care options. Mean and range of progression at each interval will also be reported. The proportions above and means for *persistent* change will also be defined as the difference between baseline and 6 months (or 3 months if no 6 month contact or patient deceased). We will similarly examine pre- and post-intervention changes over time in knowledge, attitudes, and beliefs about EOL care and prognosis, decisional conflict, and QOL using non-parametric tests among the intervention group versus controls. Pre-specified subgroup analyses will stratify change in outcomes by: condition, mistrust, and spirituality. To achieve sensitivity of around 50% (with 10% confidence intervals, e.g. CI: 40% to 60%) in the outpatient algorithm, we will need to review 150 charts of patients diagnosed with metastatic (Stage III or IV) breast, lung and colorectal cancer (75 “test positive” and 75 “test negative” cases). The controlled pilot study in Aim 3 is designed to establish: feasibility, acceptability, detect preliminary efficacy signals (changes in behavioral intent, knowledge, attitudes, beliefs, decisional conflict), and generate point/variance estimates to be used to in power calculations for a future fully-powered RCT. We propose a small pilot RCT that will include 24 patient-caregiver pairs in each arm (intervention versus a usual care control group). This will yield greater than 80% power to detect a large intervention effect defined as an absolute difference in desired primary outcome of 40% (across a range of different point estimates), and between 60-70% power to detect a more modest absolute difference of 30% between the two groups (across a range of point estimates). To ensure the ability to recruit the additional patient-caregiver pairs for the study, we will extend the enrollment period from 15 months to 18 months. Parkland Hospital providers care for more than 900 breast, lung and colon cancer patients per year, and roughly 40% are African American; consequently we believe that we will able to successfully enroll this number of participants within our 18 month timeframe.

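### Table 1's outpatient codes do not match the colorectal target: the row is labelled colon, and the colon and lung ranges start part-way through their families with no reason given

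*Combined protocol and SAP*

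**What the plan says.** **Target population.** Four places name colorectal cancer:
- Aim 1 (section 5.1.E): "advanced breast, lung, and colorectal cancer who are appropriate for advance care planning".
- D.2.1: "identify persons with stage III and IV breast, lung, colorectal, and prostate cancer".
- D.5.1, on what the daily algorithm run is for: "identify AA patients with Stage III or IV breast, lung, colorectal, prostate, or other advanced cancer for EOL care counseling".
- D.5.4, on the chart-review sample: "metastatic (Stage III or IV) breast, lung and colorectal cancer".

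Other places say colon: Hypothesis 1, the chart-review judgment in D.3 ("has Stage III/IV breast, lung, colon, prostate or other advanced cancer"), and the eligibility sentence in D.5.1 itself.

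**Code list.** Table 1, outpatient part, has three site rows:
- Colon Cancer: "C18.2-C18.9; C19".
- Breast: "C50.011-C50.929; D05.80-D05.92".
- Lung: the same ranges as in the pilot inpatient part, "C34.10-C34.92; D02.20-D02.22".

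A separate Metastases row covers C77.0 to C79.9. The table defines no code and gives no reason for where a range starts.

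**Rule and goals.** D.3 adds a stage III or IV element and leaves the Boolean combination of the elements open. It aims for sensitivity of 40-50% and ranks specificity above sensitivity. D.5.4 plans 150 charts, 75 test positive and 75 test negative.

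**The concern.** A site-code list is the entry gate of this kind of algorithm. If the list is narrower than the population in the text, the missed patients are lost before stage, treatment or symptom variables are looked at.

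Two aims depend on it. In Aim 1, the list shapes the rule whose sensitivity is estimated. If the same list also defines which charts can be drawn as test negative, the missed patients never enter the denominator and the estimate looks better than it should. In Aim 3, the refined algorithm finds the patients, and D.5.1 wants a roughly even spread across cancer diagnoses. A short colorectal list works against that.

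The colon row is also untested. The pilot in D.1 covered breast and lung cancer only, so no earlier result supports this row.

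**Working it through.** The plan gives no figure for how much of the target the code list covers, so there is nothing to reproduce. The check is a comparison of text followed by a sensitivity range.

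**1. Ranges by their numbering.** The colon row opens at C18.2, so anything numbered C18.0 or C18.1 is outside. The lung row opens at C34.10, so anything numbered C34.0 is outside. The breast C-range, by contrast, opens at C50.011. The colon row ends with C19, a category of its own. What the omitted codes stand for is not in the documents and must be read from the code book.

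**2. What the open Boolean rule does.**
- *Listed site code required together with a metastasis code or stage:* a patient with no listed site code cannot be flagged.
- *Metastasis code or stage sufficient alone:* some of these patients are recovered.
- *Listed site code required together with either metastasis or treatment:* the patient is again lost.

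The gap therefore bites under any rule that requires a listed site code.

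**3. Size, from the registry counts in D.1** (Stage IV, 2009-2011): breast 75, lung 254, colorectal 135.
- Total: 75 + 254 + 135 = 464.
- Colorectal share: 135/464 = 29.1%.

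Let *f* be the share of colorectal cases with no code inside the row. It is not given, so a range is shown.
- Share of all cases missed = 0.291 × *f*.
- Highest reachable sensitivity = 1 − 0.291 × *f*.
- Overall sensitivity = sensitivity within listed codes × (1 − 0.291 × *f*).

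| *f* (assumed) | All cases missed | Ceiling | 50% within list becomes | 40% within list becomes |
|---|---|---|---|---|
| 10% | 2.9% | 97.1% | 48.5% | 38.8% |
| 30% | 8.7% | 91.3% | 45.6% | 36.5% |
| 50% | 14.5% | 85.5% | 42.7% | 34.2% |

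**4. African American patients only.** Applying the D.1 percentages (57%, 61%, 55%) to the same counts gives 42.75 + 154.94 + 74.25 = 271.94. The colorectal share is then 74.25/271.94 = 27.3%. For *f* from 10% to 50%, 2.7-13.7% of cases are missed, and 40% becomes 38.9-34.5%.

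**5. Not in these figures.** They count colorectal cases only. Lung is 254/464 = 54.7% of the pool, so each 1% of lung cases outside the lung range would add about 0.55 percentage points to the share missed.

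**The case against.** The case on the other side has real weight.

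- **The text uses both terms.** Part of the mismatch is loose wording, and it does not prove that eligible patients are excluded. This stands, but the two terms still have to be reconciled.
- **Table 1 is not final.** It has no prostate row although prostate is a target, and D.3 promises iterative refinement. But refinement finds omitted codes only if the reviewed charts can contain them, and D.5.4 does not say how test-negative charts are drawn. The broader search in D.3 covers more record fields and 12 months of encounters. It may catch a patient who has a listed code elsewhere, but the plan does not say that it widens the list.
- **The ceiling does not bind.** At 85.5-97.1% it lies well above the 40-50% goal, and sensitivity ranks second. This stands: the goal remains reachable. The loss matters mainly if sensitivity within the list is near 40%.
- **Physicians confirm eligibility (D.5.1).** That happens after flagging, so it cannot recover patients who were never flagged.

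Three stronger readings are tempting, and the documents do not support them.

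1. *The row covers colon only.* That fits the label, but C19 lies outside C18. Without definitions, rectal coverage cannot be settled from the documents.
2. *The D05 and D02 codes are in situ disease, so ineligible patients will be flagged.* The documents do not define these codes. If a metastasis code or stage III/IV is also required, a D-code alone flags nobody. The pilot rule did require metastatic disease, together with low albumin. D.5.1 also allows some stage I and II patients. No loss of specificity can be computed. Deleting the D-codes outright could even drop a patient whose only site code is a D-code but who also has a metastasis code.
3. *A known share of patients can never be flagged.* Both the share and the rule are open.

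**Conclusion.** The concern holds as a mismatch between the code list and the stated population. The text targets colorectal cancer; Table 1 offers a colon row limited to C18.2-C18.9 and C19. The colon and lung ranges start part-way without explanation, and the text alternates between two terms.

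The consequence is conditional. If a listed site code is required, patients coded outside the ranges are missed. The number is unknown; over the assumed 10-50% of colorectal cases, the overall loss runs from small to about one case in seven. This rests on three assumptions: the Stage IV registry mix stands for Stage III/IV outpatients, all breast and lung cases are inside their ranges, and sensitivity within the list is the same for each cancer.

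It does not invalidate the pilot. It is worth correcting before validation because the reported sensitivity could otherwise hide the gap.

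**What to change.** Before the outpatient rule is validated:

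1. Use colorectal throughout: Hypothesis 1, D.3, the D.5.1 eligibility sentence and the Table 1 row label.
2. Extend the Table 1 row to the full colon, rectosigmoid and rectal code families, and open the colon and lung ranges at their first code. Have a coder check each range against the code book and, if possible, the codes carried by registry Stage III/IV cases.
3. Check whether the D05 and D02 codes belong in a Stage III/IV rule. Keep them only if a metastasis code or stage III/IV is also required.
4. State the rule that combines site, metastasis, stage and treatment elements.
5. Draw the 75 test-negative charts from a frame that the code list does not define, for example the tumor registry that D.1 already uses, so that missed cases count in the estimated sensitivity.

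The cost is an edit to one table and the query, a few wording changes, some coder time, and the work of drawing a registry-based chart frame. The planned 150 charts and the Aim 3 sample can stay as they are.
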